5.7 Other Analyses

Not applicable.

5.8 Exploratory Analyses

Other exploratory analyses may be conducted as appropriate. Any exploratory analyses that are performed will be appropriately titled/labelled as exploratory and will be clearly distinguished from planned analyses when results are reported in the Clinical Study Report.

5.9 Extension Phase Analyses

The statistical methods for the Extension Phase will not be described in this SAP but will be described in a separate SAP.

6 INTERIM ANALYSES

After every 4th subject completes the Maintenance Period an interim analysis (safety, tolerability, and PK) will be conducted where dose-normalized exposure will be compared to that observed in other studies in subjects between ≥ 2 and < 18 years of age for evidence of

systematic deviations potentially warranting dose adjustment in this age group or for other subjects enrolled in the study.

All data from the Pretreatment and Treatment Phases (Core Study) will be analyzed when all subjects have completed the Maintenance Period. In addition, data from the Pretreatment, Treatment, and Extension Phases will be analyzed when all subjects have completed the Extension Phase.

An independent Data Monitoring Committee (DMC) will be constructed to monitor the safety data. The responsibilities, membership, and purpose of the DMC, the timing of the meeting(s), and an outline of the plan for review of the safety data are documented in the DMC Charter.

7 CHANGES IN THE PLANNED ANALYSES

There are no major changes in the planned analyses from the protocol at the time of the finalization of this SAP.

8 DEFINITIONS AND CONVENTIONS FOR DATA HANDLING

8.1 EFFICACY DATA HANDLING

8.1.1 Baseline efficacy Data

Baseline seizure frequency per 28 days will be calculated two ways.

For the primary analysis of seizure endpoints, baseline seizure frequency per 28 days will be calculated using seizure data from the 2-week Pretreatment Phase. Seizures per 28 days during these 2-week pretreatment phase will be calculated as the number of seizures during this interval divided by the number of days during this interval multiplied by 28.

Data is also collected over the 4-week interval prior to visit 1 for the days when subject experienced seizures. For the secondary analysis of seizure endpoints, baseline seizure frequency per 28 days during the 2-week Pretreatment Phase plus the 4 weeks prior will be used. Baseline seizure frequency for this analysis will be calculated by taking the average of seizure per 28 days from the 2-week Pretreatment Phase and seizures per 28 days from the 4 weeks interval prior to Visit 1. Seizures per 28 days during the 4-week prior interval will be calculated by summing the number of reported seizures during the 4-week (28-day) interval prior to visit 1.

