## **Treatment Phase:**

- Seizure Frequency: Percentage change in 28-day seizure frequency during the Treatment Phase and the Extension Phase, compared to Baseline. The primary analysis will use data prospectively collected during the 2-week Pretreatment Phase to calculate baseline 28-day seizure frequency. A secondary analysis will use data prospectively collected during the 2-week Pretreatment Phase plus data retrospectively collected during the 4 week period before Visit 1 to calculate baseline 28-day seizure frequency. Seizure frequency per 28 days will be calculated as the number of seizures over the entire time interval divided by the number of days in the interval and multiplied by 28. (revised per Amendment 02)
- Responder Rate: A responder is defined as a subject with atleast 50% decrease in 28-day seizure frequency while on treatment when compared to Baseline. Analyses using the 2 different baseline definitions above will be performed. For subjects who discontinue the

study with less than 8 weeks of seizure data in the Maintenance Period, the last 8 weeks of data after the first dose (or entire treatment duration if <8 weeks of data are available) will be used in lieu of Maintenance Period.

- Seizure-free status: The proportion of subjects who are seizure-free during the Maintenance Period
- CGI-C

Details on efficacy analyses for the Extension Phase can be found in Appendix 3.

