5.4 Exploratory Efficacy Analyses

This study is designed to assess PK and provide safety, tolerability and efficacy data in children with epilepsy aged 1 month to less than 4 years. Given the small sample size and lack of placebo or comparator, it will not be possible to draw definitive conclusions regarding the efficacy of perampanel oral suspension for the population in this study. As such, no formal statistical tests will be performed. Summary statistics will be displayed for all efficacy parameters in the Full Analysis Set unless stated otherwise.

The primary analysis will use data from the Pretreatment Phase to calculate baseline 28-day seizure frequency. A secondary analysis will use data from the Pretreatment Phase plus data from the 4 weeks prior to Visit 1 to calculate baseline 28-day seizure frequency. Seizure frequency will be based on the number of seizures per 28 days, calculated as the number of seizures over the time interval multiplied by 28 and divided by the number of days in the interval. Seizure frequency will refer to the overall seizure type, unless stated otherwise, obtained by combining across all seizure types.

Post-baseline data reported only during the **on-treatment** duration will be analyzed. The on-treatment duration is defined as follows:

• For diary data: The duration between the day of first study drug dose and the last

day of study drug dose, inclusive.

• For CGIC data: The duration after the day of first study drug dose up to 7 days after the last study drug dose, inclusive.

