5.4.2 Secondary Exploratory Efficacy Analyses

Secondary analyses for the percent change and responder rate endpoints in seizure frequency will use seizure data from the Pretreatment Phase plus the data from the 4 weeks prior to Visit 1 to calculate baseline 28-day seizure frequency.

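### The SAP's secondary baseline averages the 2-week and 4-week seizure rates equally, whereas the protocol pools seizures over days, and the change is not disclosed

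*SAP*

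**What the plan says.** Protocol 9.7.1.6 sets two baselines. The primary one uses the 2-week Pretreatment Phase alone. For the other: "A secondary analysis will use data prospectively collected during the 2-week Pretreatment Phase plus data retrospectively collected during the 4 week period before Visit 1". The next sentence gives the formula: "Seizure frequency per 28 days will be calculated as the number of seizures over the entire time interval divided by the number of days" in that interval, times 28.

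SAP 5.4 names the same two baselines and then repeats a count-over-days formula, "calculated as the number of seizures over the time interval multiplied by 28 and divided by the number of days in the interval". SAP 5.4.2 says that the secondary percent-change and responder analyses "will use seizure data from the Pretreatment Phase plus the data from the 4 weeks prior to Visit 1".

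SAP 8.1.1 gives the working rule for the secondary baseline: "taking the average of seizure per 28 days from the 2-week Pretreatment Phase and seizures per 28 days from the 4 weeks interval" before Visit 1. The Pretreatment rate is seizures divided by days, times 28. The earlier rate is obtained by "summing the number of reported seizures during the 4-week (28-day) interval prior to visit 1".

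SAP 7 states that there are no major changes from the protocol and does not mention this rule. SAP 9 places programming rules in separate documents, which were not available.

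**The concern.** The protocol's formula follows directly on the sentence that names the combined data, and it refers to the whole interval. Applied to those data it pools seizures and days, so every day counts equally. The SAP average gives each period half the weight whatever its length. With 14 Pretreatment days, each of them counts twice as much as each of the 28 earlier days, and the imbalance grows as Pretreatment days fall.

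The SAP would therefore report a different baseline from the one the protocol defines, and its reader is not told. A programmer working from the protocol and one working from SAP 8.1.1 would produce different baselines, and some different responder classifications, for the same subjects.

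**Working it through.** The plan states no figure to reproduce, so the check compares the two formulas.

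**Notation.** *a* = seizures in *d* Pretreatment days; *b* = seizures in the 28 days before Visit 1.

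- SAP 8.1.1: (28*a*/*d* + *b*)/2. At *d* = 14 this is *a* + *b*/2.
- Protocol 9.7.1.6: 28(*a* + *b*)/(*d* + 28). At *d* = 14 this is 2(*a* + *b*)/3.

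The nominal *d* is 14. Protocol Table 4 allows Visit 2 a window of 2 days either way, so *d* = 12 is the shortest interval if that window is kept. It is not a floor for the calculation: the Pretreatment Phase lasts up to 2 weeks, and SAP 8.1.2 counts only days with valid entries. I therefore add *d* = 7 as an assumed case.

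**Per subject.** Let the 2-week rate be *k* times the 4-week rate. The ratio of SAP to protocol is [(*k* + 1)/2] / [(*kd* + 28)/(*d* + 28)]. The limits, with no seizures in one interval, are (*d* + 28)/56 and (*d* + 28)/(2*d*).

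| *d* | *k* = 0.5 | *k* = 2 | No Pretreatment seizures | No earlier seizures |
|---|---|---|---|---|
| 14 | -10.0% | +12.5% | -25% | +50% |
| 12 | -11.8% | +15.4% | -29% | +67% |

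Two examples at *d* = 14, with assumed counts:

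- *a* = 10, *b* = 10. SAP: (20 + 10)/2 = 15.0. Protocol: 28 × 20/42 = 13.33. With 7 seizures per 28 days on treatment the change is -53.3% (responder) under the SAP and -47.5% (non-responder) under the protocol.
- *a* = 5, *b* = 20. SAP: (10 + 20)/2 = 15.0. Protocol: 28 × 25/42 = 16.67. With 8 on treatment the change is -46.7% (non-responder) under the SAP and -52.0% (responder) under the protocol.

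**Across subjects.** The documents give no seizure rates, so these inputs are assumptions: independent Poisson counts, 4, 8, 16 or 32 seizures per 28 days at baseline, a 30%, 40% or 50% reduction on treatment, a 28-day Maintenance Period, and subjects with no baseline seizures excluded. Exact enumeration over the 12 settings, as SAP minus protocol:

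| *d* | Net responder rate (points) | Subjects whose status changes | Median percent change (points) |
|---|---|---|---|
| 14 | -1.28 to +0.14 | 2.62% to 5.48% | -0.55 to +1.38 |
| 12 | -1.25 to +1.19 | 3.29% to 6.90% | -4.76 to +1.03 |
| 7 | -1.19 to +1.58 | 6.21% to 12.00% | -5.36 to +4.17 |

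At the planned maximum of 50 subjects (24 + 26), the largest net shift is 0.0128 × 50 = 0.64 of a subject at *d* = 14 and 0.0158 × 50 = 0.79 at *d* = 7. The full analysis set may be smaller. The -4.76 at *d* = 12 occurs only at 4 seizures per 28 days, where the possible values are coarse.

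**Precision.** With a constant Poisson rate *L* per 28 days, the SAP average has variance (*L*/4)(28/*d* + 1) and the pooled rate 28*L*/(*d* + 28). At *d* = 14 these are 0.750*L* and 0.667*L*, so the average has 12.5% more variance. At *d* = 7 they are 1.25*L* and 0.80*L*, or 56% more.

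**The case against.** The strongest reply is that the protocol leaves analysis detail to the SAP, and that its formula is one general sentence that does not say how to join a prospective and a retrospective interval. SAP 8.1.1 uses the protocol's data, applies count over days within each interval, and states the combining step openly. SAP 7 denies only major changes, which may be literally true here. More weight on diary days can also be defended, because the earlier period is less complete: "Data is also collected over the 4-week interval prior to visit 1 for the days when subject experienced seizures". Summing days across the two periods is therefore not quite clean, and the pooled formula needs a fixed 28-day denominator. Finally, the summaries are exploratory, and SAP 5.4 itself says that "it will not be possible to draw definitive conclusions regarding the efficacy of perampanel oral suspension".

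Much of this stands. The consequence is small, SAP 7 contains no demonstrably false statement, and neither formula is shown to be biased. SAP 5.4 contradicts SAP 8.1.1 only if its interval means the combined six weeks. But the protocol does supply a formula, directly after naming the combined data and for the entire interval, and nowhere does it provide for averaging two rates. A rule that gives a different number whenever the two rates differ is more than added detail. The SAP does not give data quality as its reason for the weighting. The fixed 28-day denominator is already what SAP 8.1.1 uses for the retrospective period.

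**Conclusion.** The concern holds and is minor. The firm conflict is between protocol 9.7.1.6 and SAP 8.1.1, on the plain reading that an average with no stated weights is a simple mean. As the specific rule, SAP 8.1.1 would normally govern programming; the unseen programming documents could say otherwise.

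Individual baselines can differ by 10% or more and some subjects change responder status, but the changes largely offset. The net shift stays below one subject among 50 in every setting examined. Those ranges rest on the assumed Poisson counts and rates; real seizure counts may cluster more. Only the secondary versions of two descriptive summaries are touched, with no formal tests.

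**What to change.** In SAP 8.1.1, define the secondary baseline as 28 × (Pretreatment seizures + seizures reported in the 4 weeks before Visit 1) / (valid Pretreatment diary days + 28). Keep the retrospective denominator at 28, because only seizure days are recorded there. This restores the protocol's rule and, under the Poisson assumption, gives a less variable baseline. It can also be computed for a subject with no valid Pretreatment days, for whom the average is undefined. The cost is one SAP sentence and one derivation line.

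If the equal-weight average is intended, list it with its reason in SAP 7 and add a clause to SAP 5.4 so that the two sections agree. That settles the disclosure but leaves the departure from the protocol in place.

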8.1.2 Handling of Missing Efficacy Data, Drop-outs, and Outliers

Only days with valid seizure counts will be used in the calculations of seizures frequency per 28 days. A day is said to have a valid seizure count if either (1) "No" was the answer to the one of questions "Did the subject experience any <seizure category> seizures?" in the Seizures Diary Log or (2) other seizure counts were reported for that day.

In subjects where dose tapering was done before discontinuation, safety data for the entire exposure to study drug will be included in the safety analyses. However, seizure data during tapering will be excluded from the efficacy analyses.

Details on handling efficacy data for early dropouts is provided in section 5.3.5.

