5.4.3 Other Exploratory Efficacy Analyses

The percent change in 28-day seizure frequency during the Titration Period (no imputation) and Maintenance Period (using LOCF-type imputation described in Section 5.3.5) will also be summarized.

Percent change, seizure free and responder rate in 28-day seizure frequency analyses will also be repeated for each seizure type, as appropriate for subjects who have that seizure type during the baseline. Subjects who develop new seizure types during the study will be summarized by seizure type separately.

CGI-C scores at EOT compared to baseline will be summarized using frequency table. The EOT value is the last non-missing value while on treatment.

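### SAP 8.1.2, read literally, accepts a partly completed diary day as valid, so an unanswered seizure category can act as a zero in the exploratory seizure endpoints

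*SAP*

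**What the plan says.** SAP 8.1.2 sets the filter: "Only days with valid seizure counts will be used in the calculations of seizures frequency per 28 days". It gives two alternative routes to a valid day. On the first, 'No' "was the answer to the one of questions" about a named seizure category in the diary log. On the second, "other seizure counts were reported for that day". Neither route mentions the other categories.

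SAP 5.4 defines the frequency, "calculated as the number of seizures over the time interval multiplied by 28 and divided by the number of days in the interval", with the main count "obtained by combining across all seizure types". SAP 5.4.3 adds that the percent change, seizure-free and responder analyses "will also be repeated for each seizure type". SAP 8.1.1 computes the primary baseline "using seizure data from the 2-week Pretreatment Phase", so the same day filter applies before and during treatment. SAP 5.3.5 makes seizure-free status depend on completing the Maintenance Period and is silent on diary completeness.

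No section says whether an unanswered category on a valid day is a zero, a missing value, or a reason to drop the day for that type.

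**The concern.** The log asks its question by seizure category, but validity is defined by day. If a parent answers 'No' for one type and leaves another blank, the day passes the filter. Summing over types and dividing by valid days then gives the same result as if the blank had been a zero. The second route has the same gap, because a count for one type validates the day for all.

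The by-type analyses show it most plainly. A day made valid by an answer about type A would enter the type B frequency with no type B information on it. At stake are the diary-based efficacy results in a study with no comparator arm, where nothing would offset an artefact of diary completion.

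**Working it through.** The plan states no partial-entry rate and no bias, so there is no figure to reproduce. The check applies the SAP formula with SAP 8.1.2 read literally (days in the interval taken as valid days).

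**Inputs.** From the SAP: frequency = seizures / valid days × 28, and a 2-week primary baseline (14 days). Assumed, because the documents do not give them: *f*, the share of a period's days with a category blank but the day still valid; *s*, the share of the child's seizures in that category; and one seizure a day.

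**Step 1: one period.** Observed frequency = true frequency × (1 − *s* × *f*). With complete entries, 14 / 14 × 28 = 28.0. With 2 partial days and *s* = 50%, one seizure goes unrecorded and (14 − 1) / 14 × 28 = 26.0.

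| Partial days of 14 | Literal rule, *s* = 100% | Literal rule, *s* = 50% | Every category required |
|---|---|---|---|
| 1 | 26.0 (7.1% low) | 27.0 (3.6% low) | 28.0 |
| 2 | 24.0 (14.3% low) | 26.0 (7.1% low) | 28.0 |
| 4 | 20.0 (28.6% low) | 24.0 (14.3% low) | 28.0 |
| 7 | 14.0 (50.0% low) | 21.0 (25.0% low) | 28.0 |

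The last column assumes that partial days resemble the others. In a by-type analysis of the blank category, *s* is 100% by construction. The error is zero if no day is partial or if no seizures fall in the blank category; it is never an overcount.

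**Step 2: percent change.** Observed change = (1 + true change) × (1 − *s* × *f* on treatment) / (1 − *s* × *f* at baseline) − 1. With *s* = 100%:

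| True change | *f* at baseline | *f* on treatment | Observed change |
|---|---|---|---|
| 0% | 25% | 25% | 0% |
| 0% | 0% | 25% | −25% |
| 0% | 0% | 50% | −50% (false responder) |
| 0% | 10% | 25% | 0.75 / 0.90 − 1 = −16.7% |
| 0% | 25% | 0% | 1 / 0.75 − 1 = +33.3% |
| −40% | 0% | 16.7% | 0.60 × 0.833 − 1 = −50% (reaches the responder threshold) |

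With *s* = 50%, a complete baseline and no true change, *f* of 10%, 20% or 30% on treatment gives −5%, −10% or −15%.

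**Step 3: seizure freedom.** This status has no baseline term. An unrecorded seizure on a day that passes the filter can turn a child who had seizures into a seizure-free one, never the reverse.

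**Step 4: would dropping every partial day be safe?** Take a 28-day Maintenance Period with one recorded seizure, on a day when another category is blank. The literal rule gives 1 / 28 × 28 = 1.0. Dropping the day gives 0 / 27 × 28 = 0, and a child with a documented seizure could be called seizure-free. Blanket exclusion is therefore not an acceptable remedy.

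**The case against.** The strongest reply is that the plan never says what is attributed to it. The first route is ungrammatical and may have been meant as an answer to each of the questions. The category placeholder could also be read as applying the rule category by category, which would remove the by-type problem. The log layout is not in the documents, and SAP section 9 puts derivation rules in separate specifications, so a blank category on a completed day may not even be possible. Protocol 9.5.1.3 asks for daily completion with every seizure recorded and for physician review of the diary at all visits, and scheduled telephone calls check that diaries are kept up. A blank may also be a type the child never has, for which zero is right.

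Much of this stands. The zero is inferred from the arithmetic, not stated, and the safeguards make hidden seizures less likely. They do not close the gap. Mending the first route leaves the second, which validates a day on any count. The physician review is there to get seizure classification right, and the counselling trigger concerns whole entries missed on at least three days running, not partly filled days. A rule that programmers must guess at needs rewording in any case.

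A reader might go further and infer that frequencies are in fact undercounted and that the error favours perampanel. The documents do not support that. They report no partial entries, and the rule covers baseline and treatment diaries alike. Equal completeness leaves percent change unaffected, and poorer completeness at baseline works against the drug, as Step 2 shows.

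**Conclusion.** The concern holds as a defect in a stated rule, conditional on partly completed days occurring. On the literal reading, overall and by-type frequencies can be understated by *s* × *f*, seizure-free rates can only be inflated, and percent change and responder status can be biased in either direction or not at all. Every percentage above rests on assumed partial-entry rates.

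The reach is limited. SAP 5.4 treats efficacy as exploratory, without formal tests and without definitive conclusions; the primary PK endpoint and the safety analyses are untouched. Within that limit single children matter: results are shown by age cohort, and Protocol 9.1 plans minimums of 5 or 6 in the three infant cohorts, so in a cohort of that size one misclassified child moves a rate by 1/6 to 1/5, about 17 to 20 percentage points.

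**What to change.** Reword SAP 8.1.2 as follows.

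- **By-type analyses:** a day is valid for a type only if that category has 'No' or a count.
- **Overall frequency:** a day is valid if every category applicable to that child has 'No' or a count. Applicable means the types in the child's epilepsy history or reported during the study, so a blank for a type the child has never had does not cost the day.
- **Seizure-free status:** any day with a recorded seizure counts against it, whether or not the day is otherwise complete.
- **Sensitivity:** show frequency results with partly answered days that carry a recorded count both included and excluded.
- **Reporting:** tabulate the number of partly answered days by period, so that a reader can see whether the problem arose and in which direction it would act.

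The cost is somewhat fewer valid days and a small amount of extra programming. No new data are needed.

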8.2 SAFETY DATA HANDLING

8.2.1 Baseline safety Data

The baseline value for all safety endpoints will be the last non-missing measurement prior to the first dose of study drug.

8.2.2 Visit Windows for Safety Data

For the by-visit summaries of clinical laboratory data, vital signs, ECG, and growth parameters, visit windows will be applied to determine into which study week scheduled, unscheduled, and early discontinuation data were actually recorded, relative the first dose of study drug (Day 1). The aim of using windows for visits is to include the maximum amount of data; hence windows will split at the midpoint between visits. It gives the mapping of relative day ranges to study week, as well as the target day of a given study week. Mappings of relative day ranges to study week will be done for clinical laboratory data, vital signs, ECG data and growth parameter. Tables 1&2 below provide the mapping of relative day ranges to study week for non-AE safety variables. The on-treatment duration for laboratory, vital signs, and ECG data is considered to begin on the day of the first dose of study drug and ends 14 days after the last dose of study drug, inclusive.

		Study Day Range (Relative to First Dose of	
Study Period	Study Week	Study Drug)	Target Day
Pretreatment	Baseline	Day ≤1 ^a	≤1
Treatment (Titration)	Week 2	$2 \le Day \le 21$	15
Treatment (Titration)	Week 4	$22 \le \text{Day} \le 42$	29
Treatment (Titration)	Week 8	$43 \le Day \le 70$	57
Treatment (Titration)	Week 12	$71 \le \text{Day} \le 91$	85
Treatment (Maintenance)	Week 14	$92 \le \text{Day} \le 105$	99
Treatment (Maintenance)	Week 16	$106 \le \text{Day} \le 119$	113
Treatment (Follow-Up)	Week 99	120 or $LD \le Day \le 999^{b}$	141

 Table 1. Visit Windows – Non-EIAED Subjects

- a: All assessments at Visit 2 were to be performed prior to first dose of study drug; results from these assessments will be regarded as Pretreatment values in the analyses.
- b: The last non-missing value measured in the treatment duration will be handled as the data of EOT of the core study.
- LD = Last Dose (whichever occurs first)

Table 2. Visit Windows – EIAED Subjects

Study Period	Study Week	Study Day Range (Relative to First Dose of Study Drug)	Target Day
Pretreatment	Baseline	Day ≤1 ^a	1
Treatment (Titration)	Week 2	$2 \le Day \le 21$	15
Treatment (Titration)	Week 4	$22 \le \text{Day} \le 42$	29
Treatment (Titration)	Week 8	$43 \le Day \le 70$	57
Treatment (Titration)	Week 12	$71 \le \text{Day} \le 98$	85
Treatment (Titration)	Week 16	$99 \le \text{Day} \le 119$	113
Treatment (Maintenance)	Week 18	$120 \le \text{Day} \le 133$	127
Treatment (Maintenance)	Week 20	$134 \le \text{Day} \le 154$	141
Treatment (Follow-Up)	Week 99	155 or $LD \le Day \le 999^{b}$	169

a: All assessments at Visit 2 were to be performed prior to first dose of study drug; results from these assessments will be regarded as Pretreatment values in the analyses.

b: The last non-missing value measured in the treatment duration will be handled as the data of EOT of the core study.

LD = Last Dose (whichever occurs first)

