#### Table 4Schedule of Procedures/Assessments in Study E2007-G000-238: Core Study – Non-EIAED Subjects

#### Table 4Schedule of Procedures/Assessments in Study E2007-G000-238: Core Study – Non-EIAED Subjects

Phase						Treatn					
Period	Pretreatment	'retreatment Titration						Maintenance		Early Discontinuation	Unscheduled
Visit	1	2 b	3 b	4 c	5°	6 c,d,e	7°	8 c,f			
Week	-2	0	2	4	8	12	14	16	20		
Days	-14	1	15	29	57	85	99	113	141		
Procedures/Assessments											

AE = Adverse event, AED = Anti-epileptic drug, CGI-C = Clinical Global Impression of Change, CGI-S = Clinical Global Impression of Severity, CLIA = Clinical Laboratory Improvement Amendments, CRF = case report form, EAP = extended access program, ECG = electrocardiogram, EOT = end of treatment, fT3 = free triiodothyronine, fT4 = free thyroxine, IGF-1 = insulin-like growth factor-1, PK = pharmacokinetics, SAE = serious adverse event, TSH = thyroid-stimulating hormone.

a: To be done within ±6 days of the scheduled visit. Visit applies only to those subjects who complete the Treatment Phase but do not roll-over into the Extension Phase and those subjects who discontinue the study early for any reason after Visit 2 and before Visit 8.

- b: To be done within  $\pm 2$  days of the scheduled visit.
- c: Visits should be done within ± 3 days of the scheduled visit. There must be at least 10 days of treatment between Visits 3 and 4, 4 and 5, and 5 and 6.
- d: Upon successful completion of Visit 6, subjects will begin the Maintenance Period of the study.
- e: No dose titration is allowed at this visit or future visits.
- f: Visit 8 will be considered the first visit of the Extension Phase for subjects who choose to continue into the Extension Phase.

g: For clinic visits other than those specified, physical and complete neurological exams, including evaluation of the cranial nerves, motor, sensory, brainstem, cerebellar, and autonomic functions, will only be performed when there is a complaint from the parent/guardian.

- h: Two measurements of height/length should be taken. Each measurement should be recorded as a separate entry on the Vital Sign CRF.
- i: Only for those subjects who roll-over into the Extension Phase.
- j: Unused study drug to be retrieved and study drug dispensed only for subject requiring dose increases at Unscheduled Visits.
- k: To include the number and type of seizures for the 4 weeks before the Pretreatment Phase.

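### SAP Table 1 ends the non-EIAED Week 16 safety window at Day 119, where the SAP's own midpoint rule gives Day 126; the effect is confined to rare by-visit values

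*SAP*

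**What the plan says.** SAP 8.2.2 sets out how non-AE safety data are placed in study weeks: "visit windows will be applied to determine into which study week scheduled, unscheduled, and early discontinuation data were actually recorded". Its stated aim is to keep as much data as possible, and the rule that follows is "hence windows will split at the midpoint between visits".

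- **Table 1 (non-EIAED):** Week 16 runs from Day 106 to Day 119, target Day 113, labelled Maintenance. Follow-Up starts at Day 120 or last dose, target Day 141.
- **Table 2 (EIAED):** the corresponding last Maintenance window, Week 20, runs from Day 134 to Day 154, target Day 141. Follow-Up starts at Day 155 or last dose, target Day 169.
- **Both tables** carry the note "LD = Last Dose (whichever occurs first", so Follow-Up begins at the earlier of the fixed day and the last dose. Footnote b adds: "The last non-missing value measured in the treatment duration will be handled as the data of EOT of the core study".

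SAP 8.2.3 prefers the scheduled assessment when several fall in one window. It treats a week as missing when no observation falls in that week's window.

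For Visit 8 (Day 113), Protocol Table 4 states: "Visits should be done within ± 3 days of the scheduled visit". For the Follow-Up Visit (Day 141): "To be done within ±6 days of the scheduled visit".

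**The concern.** The text of SAP 8.2.2 and one row of its Table 1 disagree, and a programmer cannot satisfy both. As printed, a non-EIAED value taken 7 to 13 days after the Week 16 target is labelled Follow-Up. An EIAED value equally late after its Week 20 target is kept as end of Maintenance. Both groups have the same 28-day gap between the last Core treatment visit and Follow-Up.

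What could be lost is a by-visit value. Under SAP 8.2.3, a child with no observation on Days 106 to 119 is missing at Week 16. Height and head circumference are the most exposed. After the first dose, Protocol Table 4 schedules them in the Core Study only at Visit 8 or early discontinuation, and not at Follow-Up, so a late value would move to a row where none is planned. Growth is a secondary objective. The cohorts under 24 months have recruitment minima of only 5 or 6.

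**Working it through.** **Inputs.** Target days and printed windows come from SAP Tables 1 and 2. Visit tolerances come from Protocol Table 4, footnotes a and c.

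**Formula.** For adjacent targets t1 and t2, the midpoint is m = (t1 + t2)/2. The printed tables give the midpoint day to the later window, so the earlier window ends at m − 1.

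**Table 1, non-EIAED**

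| Targets | Midpoint | End by rule | Printed end |
|---|---|---|---|
| 15, 29 | 22 | 21 | 21 |
| 29, 57 | 43 | 42 | 42 |
| 57, 85 | 71 | 70 | 70 |
| 85, 99 | 92 | 91 | 91 |
| 99, 113 | 106 | 105 | 105 |
| 113, 141 | 127 | 126 | **119** |

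**Table 2, EIAED**

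| Targets | Midpoint | End by rule | Printed end |
|---|---|---|---|
| 15, 29 | 22 | 21 | 21 |
| 29, 57 | 43 | 42 | 42 |
| 57, 85 | 71 | 70 | 70 |
| 85, 113 | 99 | 98 | 98 |
| 113, 127 | 120 | 119 | 119 |
| 127, 141 | 134 | 133 | 133 |
| 141, 169 | 155 | 154 | 154 |

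The rule reproduces 12 of the 13 post-baseline ends. The exception is short by 126 − 119 = 7 days.

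**Could another convention give 119?** If the midpoint day went to the earlier window, the last Table 1 end would be 127 and the other 12 would each be off by one day. The Baseline/Week 2 split (Day 1 against Day 2) also departs from the midpoint, (1 + 15)/2 = 8. It is the same in both tables, and footnote a explains it: Visit 2 assessments precede the first dose.

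**What would make 119 right?** A split between Days 119 and 120 implies a next target of 2 × 120 − 113 = Day 127. Table 2 has such a visit; non-EIAED children do not.

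**Window lengths.** Printed: 119 − 106 + 1 = 14 days. By rule: 126 − 106 + 1 = 21 days. EIAED counterpart: 154 − 134 + 1 = 21 days.

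**Reach.** An on-time Visit 8 falls on Days 110 to 116 (113 ± 3), inside the window either way. An on-time Follow-Up Visit falls on Days 135 to 147 (141 ± 6), so Days 120 to 126 belong to neither visit. The earliest Visit 8 affected is on Day 120, which is 120 − 113 = 7 days after target and 4 days beyond its tolerance.

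**The case against.** The case against does not dispute the arithmetic; it disputes the consequence, and most of it stands.

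- **Last-dose clause.** Values on or after the last dose are Follow-Up in both tables whatever the fixed day. That covers most early-discontinuation values, and normally children who finish the Core Study without entering the Extension. Moving Day 119 to Day 126 recovers none of these.
- **Unscheduled values.** Where a child has a Visit 8 value in the window, SAP 8.2.3 takes the scheduled one. An unscheduled Day 122 value would stay out of the Week 16 summary even with the wider window.
- **Children who roll over.** Visit 8 is also their first Extension visit, and the Extension has its own SAP. Values taken after an on-time Visit 8 are arguably Extension data. This does not dispose of a late Visit 8, which is still the Core end-of-Maintenance assessment.
- **Other outputs.** End-of-treatment changes and shifts, markedly abnormal laboratory values, highest/lowest shifts and QTcF categories do not use this boundary.

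A reader might infer that late Maintenance, unscheduled and early-discontinuation values are generally lost for non-EIAED children. The documents do not support that: scheduled Maintenance ends at Day 113, and the two rules above already govern most such values. Nor does the row produce a visible contrast between EIAED groups. By-visit safety tables are by age cohort, and SAP 5.3.4 names inducer displays only for demography, seizure data and TEAEs. It is also tempting to say that Day 119 was copied from Table 2. The number matches, but nothing in the documents says so.

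**Conclusion.** The Table 1 row is wrong by the SAP's own rule, and nothing in either document explains the exception. The size is minor: seven days in one window, affecting only by-visit laboratory (including by-visit shift tables), vital-sign, ECG and growth rows. A value changes label only if the child is non-EIAED, the value falls on Days 120 to 126 and before the last dose, and no scheduled value already sits in the Week 16 window. The main case is a Visit 8 at least seven days late in a child still on drug. That value is now missing at Week 16 and shown as Follow-Up, while the equivalent EIAED value is kept.

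Two assumptions matter. First, the midpoint rule is intended to govern this row as it governs the others. Second, a child who rolls over is still on drug at Visit 8 for the purpose of the last-dose clause. The tables do not say whether last dose means the last Core dose or the last dose in the study; the Core reading would narrow the effect further. The documents do not allow an estimate of how many values are involved. With cohort minima of 5 or 6, one value could alter a by-visit row, but such cases should be rare.

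**What to change.** In SAP Table 1, change the Week 16 window to Days 106 to 126 and the start of Follow-Up to Day 127 or last dose, whichever is first. Table 2 needs no change. If the shorter window is intended, add a footnote giving the reason. The cost is two numbers in one table and the matching line in the programming specification; no data collection or visit schedule is touched.
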